4. EFFICACY ENDPOINTS

- Non-inferiority of the investigational product to the FDA-approved active control for \log_{10}/cm^2 recovery of skin flora relative to Treatment Day baseline \log_{10}/cm^2 on the inguinal region at 10 minutes following application. Non-inferiority is based on a non-inferiority margin of $0.5 \log_{10}/\text{cm}^2$.
- Superiority of the active products to the negative control for \log_{10}/cm^2 recovery of skin flora relative to Treatment Day baseline \log_{10}/cm^2 on the inguinal region at 10 minutes following application. A superiority margin of $1.2 \log_{10}/\text{cm}^2$ is used.
- Number of observations for which the \log_{10}/cm^2 recovery of skin flora on the inguinal region at 6 hours following application of the study products is higher than treatment day \log_{10}/cm^2 baseline skin flora.
- The principal measure of safety will be the incidence of adverse events reported during the study and a summary of the skin irritation rating scores. A skin irritation rating of 3 post-treatment in any category (erythema, edema, rash and dryness) represents significant irritation and qualifies as an Adverse Event.

5. ANALYSIS POPULATIONS

5.1 Safety Population

The intent-to-treat (ITT) data set will be the primary data set for safety and will include all subjects randomized to a treatment group. Subjects will be analyzed in the group to

CDT

which they were randomly assigned.

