3.2 Randomization

The left and right test areas on the subject's inguinal region will be assigned according to a computer-generated randomization schedule where each will receive 1 of the 3 study products (see Table 1). Treatment randomization will be balanced between left and right sides. There are 3 different possible combinations of treatments. These are shown below in Table 2.

To provide enough subjects to meet study objectives, the treatment combinations will be randomized in a 6:1:1 ratio for combinations 1 through 3, respectively, at the single recruiting clinical facility. The details of block size will be documented in the final study report.

Baseline and post-prep samplings at 10 minutes and 6 hours will be randomized to three sites within each test area. The same test site randomization will be used on the left and right sides of a subject's body to reduce the possibility of sampling errors.

The Investigator is responsible for ensuring that the study randomization is followed. Randomization envelopes will be provided to the study site.

CDT

Table 1 Study Products

Treatment Code	Study Product	Description
SP	SoluPrep	Contains 2% w/v chlorhexidine gluconate (CHG) and 70% v/v isopropyl alcohol (IPA). 10.5-mL applicator, tinted.
SPFF	SoluPrep FF	Contains 2% w/v chlorhexidine gluconate (CHG) and 70% v/v isopropyl alcohol (IPA) in combination with an acrylate copolymer. 10.5-mL applicator, tinted.
S	Saline	Negative control. Sterile 0.9% saline. 20-mL bottle.

Table 2 Subject Treatments

Treatment Combination	Left and Right Treatment
1	SoluPrep 10.5-mL and SoluPrep FF 10.5-mL (SP + SPFF)
2	SoluPrep 10.5-mL and saline (SP + S)
3	SoluPrep FF 10.5-mL and saline (SPFF + S)

Randomization Plan:

A 3M statistician not assigned to the project will develop a randomization program and generate the randomization code list. The code list will include randomization number, left side treatment, right side treatment, baseline sample site, 10-minute sample site and 6-hour sample site. The randomization assignments will be printed and inserted into security envelopes then tightly sealed.

The Data Manager will strip the treatment assignment from the programs that are used to download the data from Clindex®. This will keep the statistician assigned to the study blinded until data lock.

CDT

Randomization Process:

For each eligible subject to be randomized, the investigator or designee will do the following:

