- Retrieve a randomization envelope with smallest available randomization envelop number.
- Record randomization number onto a Data Collection Sheet (DCS) and/or the electronic Case Report Form (eCRF).
- When the treatments are applied, record onto a DCS and/or the eCRF; left side treatment applied, right side treatment applied, baseline sample site, 10-minute sample site and 6-hour sample site.
- Subjects will continue to be randomized until a minimum of 100 observations (with a baseline that meets the Treatment Day requirement) from each of the active treatments and 30 observations from the saline control (with a baseline that meets the Treatment Day requirement) have been collected.

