9. SAFETY ANALYSIS

Adverse events and skin irritation scores will be summarized by treatment.

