- Record randomization number onto a Data Collection Sheet (DCS) and/or the electronic Case Report Form (eCRF).
- When the treatments are applied, record onto a DCS and/or the eCRF; left side treatment applied, right side treatment applied, baseline sample site, 10-minute sample site and 6-hour sample site.
- Subjects will continue to be randomized until a minimum of 100 observations (with a baseline that meets the Treatment Day requirement) from each of the active treatments and

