**[name]**

time point and calculation of return to baseline at 6 hours. These analyses cannot be done without both baseline and 10-minute recovery for treatment effect or baseline and 6-hour recovery data for return to baseline percentage calculation. The exclusion of subjects who do not meet baseline requirements and who are missing recovery data at one or both of the post-treatment sampling times makes this data set a modified intent-to-treat data set.

The baseline bacterial count requirements are in the range of 5.00 to 7.50  $\log_{10}/\text{cm}^2$  on the groin. The acceptability of each bilateral baseline will be assessed separately for inclusion in the study.

The full intent-to-treat data set (all randomized subjects) will be used for the safety analysis.

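### Safety is analysed in all randomized subjects as randomized, although the product applied to each side is recorded; side-level safety data should follow the product applied (low priority).

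*SAP*

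**What the plan says.** SAP 5.1 defines the safety set: "The intent-to-treat (ITT) data set will be the primary data set for safety and will include all subjects randomized to a treatment group". Its next sentence, split by a page break, reads "Subjects will be analyzed in the group to" and then "which they were randomly assigned". Protocol 8.3 agrees on the set: "The full intent-to-treat data set (all randomized subjects) will be used for the safety analysis". It does not say how events are attributed. Neither document defines an as-treated safety set or overrides the SAP rule elsewhere.

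Products are assigned to sides, not to whole subjects. SAP 3.2 says: "The left and right test areas on the subject's inguinal region will be assigned according to a computer-generated randomization schedule". Irritation is rated for each test area (protocol 5.3.3.3), and a post-treatment rating of 3 counts as an AE. On reporting, SAP 9 says: "Adverse events and skin irritation scores will be summarized by treatment". Protocol 8.2.2 has the same summary by product. SAP 9.1 adds a Fisher's exact test of each safety parameter between treatment groups.

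Both documents have the site record what was actually put on each side. Protocol 3.3 says: "When the treatments are applied, record onto a DCS and/or the eCRF; left side treatment applied, right side treatment applied". The randomization process in SAP 3.2 has the same instruction.

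**The concern.** A local skin reaction is caused by the product on that skin. Suppose left and right are swapped, or a product from another combination is used. An as-randomized rule applied to sides then counts the reaction against a product that was never there. For an efficacy superiority claim, dilution of this kind is conservative. For safety it is not, because on average it moves the products' rates towards each other and so favours finding no difference.

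The same definition keeps randomized but untreated subjects in the set. SAP 9.1 counts treatment-emergent AEs only from the start of study treatment, so such a subject adds to the denominator and can never add to the numerator.

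AEs and irritation scores are the trial's principal safety measures. The plan collects the variable needed for correct attribution and then specifies a rule that does not use it.

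**Working it through.** No figure in the plan depends on this rule, so there is none to reproduce. The check has two parts: what the text implies at side level, and how much one error would weigh.

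**Text, step by step**

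1. Unit of assignment: the side (SAP 3.2).
2. Unit of irritation scoring: the test area, hence the side (protocol 5.3.3.3).
3. Unit of reporting: treatment or product (SAP 9 and 9.1; protocol 8.2.2).
4. Attribution rule: the subject's randomized group (SAP 5.1).
5. To produce product-level tables under that rule, each side has to be labelled with a product. The only label consistent with an as-randomized rule is the product randomized to that side. For a misapplied side, that label is wrong.

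**Weight of one misattributed event**

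Inputs: 135 subjects expected to be treated (protocol 1.5) and allocation 6:1:1 (SAP 3.2).

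- Combination 1 (SoluPrep and SoluPrep FF): 135 × 6/8 = 101.25 subjects
- Combinations 2 and 3 (one active product and saline): 135 × 1/8 = 16.875 subjects each
- SoluPrep sides: 101.25 + 16.875 = 118.1; SoluPrep FF sides: the same
- Saline sides: 16.875 + 16.875 = 33.75
- One event, active product: 1/118.1 = 0.8 percentage points
- One event, saline: 1/33.75 = 3.0 percentage points

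Randomization continues until the evaluable counts are reached, so 135 is an expectation. If all 10 blocks of 16 in protocol 3.3 were used (160 subjects: 120, 20 and 20), there would be 140, 140 and 40 sides. The weights would then be 1/140 = 0.7 and 1/40 = 2.5 points.

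**Average effect of swaps (illustration)**

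Assume k swapped SoluPrep and saline subjects, and true event rates of 10% on SoluPrep and 1% on saline. These rates and k are assumptions; the documents give none of them.

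- Saline rate as randomized = [0.01 × (33.75 − k) + 0.10 × k] / 33.75
- SoluPrep rate as randomized = [0.10 × (118.125 − k) + 0.01 × k] / 118.125

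| k | Saline | SoluPrep | Difference |
|---|---|---|---|
| 0 | 1.00% | 10.00% | 9.00 points |
| 1 | 1.27% | 9.92% | 8.65 points |
| 5 | 2.33% | 9.62% | 7.29 points |

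The expected difference shrinks as swaps accumulate. Five swaps would be a large share of the roughly 17 subjects in that combination, so the last row is an extreme case.

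**Untreated subjects**

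With u untreated subjects added to 135 treated, AE rates fall by a relative u/(135 + u). That is 1/136 = 0.7% for u = 1 and 5/140 = 3.6% for u = 5. The documents give no value for u.

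**The case against.** - **SAP 5.1 speaks of subjects and groups, not sides.** The example randomization table in protocol 3.3 uses treatment group for the product combination, and on that meaning a left/right swap leaves the subject in the same group. A reader might infer that the SAP explicitly attributes safety by the product randomized to each side; it does not, and that is an inference from the product-level summaries. This part stands. But on the combination reading, SAP 5.1 gives no rule for attributing side-level scores to products, and a product from another combination would still be misattributed. The sentence needs changing on either reading.

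- **The error need not flatter the investigational product.** A reader might infer that the rule always hides harm. For a single swap it does not. Three quarters of subjects receive both active products, and a swap there can move a reaction onto SoluPrep as easily as off it. Only the average effect is towards no difference.

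- **Untreated randomized subjects should be few.** The subject number is assigned on Treatment Day, after the screening counts have qualified the subject, and application follows baseline sampling in the same visit. Treatment Day plates incubate for about 72 hours, so a failed baseline count cannot stop application. An untreated subject also has no post-treatment irritation score, so only AE denominators are affected.

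- **A misapplication would be traceable in part.** Deviations are summarized and listed (SAP 7.2), AEs are listed individually (SAP 9.1), and package labels carry a treatment code and the subject number (protocol 3.4.2, 3.4.3 and 14.2). This lowers the risk that a reaction goes unnoticed. It does not correct the planned tables or the Fisher's test.

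**Conclusion.** The point holds as a low-priority correction. The plan states an as-randomized rule for safety, nothing overrides it, and the data for attribution by applied product are already collected. Carried to side level, the rule charges a reaction on a misapplied side to the wrong product.

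The size is about 0.8 percentage points per event for an active product and about 3.0 for saline. This assumes 135 treated subjects, the 6:1:1 split, and an event that can be located to a side. A reader might take 30 as the saline denominator. That figure is the minimum number of efficacy-evaluable saline observations, and the safety set is not restricted by baseline count.

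The documents give no rate of application errors. If it is zero, as-randomized and as-applied results are identical for treated sides. The documents therefore do not support a claim that the safety results will be biased, only that the rule is the wrong one if an error occurs. No efficacy conclusion, sample size or stated figure is affected.

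**What to change.** In SAP 5.1 and protocol 8.3:

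1. Define the safety set as all subjects and sides to which a study product was applied.
2. Attribute side-level AEs and irritation scores to the product recorded as applied to that side.
3. Report AEs that cannot be located to one side at subject level, by the pair of products received. This rule is needed because every subject receives two products.
4. List every discrepancy between randomized and applied product.

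The cost is a few sentences in each document and one listing. The applied product is already recorded for each side, so no new data on treatment are needed.

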5.2 Modified Intent-To-Treat Population (MITT)

A MITT data set will be used for primary efficacy analyses. All subjects who meet baseline requirements on a bilateral side will be included in the analysis for that bilateral side. However, the primary analyses involve a linear regression at the 10-minute post-treatment time point and calculation of return to baseline at 6 hours. These analyses require both baseline and 10-minute recovery for treatment effect or baseline and 6-hour recovery data for return to baseline percentage calculation. There is no scientific basis for imputation of these missing values. Fortunately, missing values are not expected. There was no missing data for the 2346 microbiological samples taken in the pivotal study conducted at this site for SoluPrep FF. The exclusion of subjects who do not meet baseline requirements and who are missing recovery data at either the 10-minute sampling time point or the 6-hour sampling time point (post-treatment) times makes this data set a modified intent-to-treat data set.

The baseline bacterial count requirements are in the range of 5.00 to 7.50 \log_{10}/cm^2 on the groin. The acceptability of each bilateral baseline will be assessed separately for inclusion in the study.

5.3 Per-Protocol Population

A second per-protocol (PP) data set will be defined excluding any subjects with major deviations including lack of compliance

A treatment side will be excluded from the modified intent-to-treat population that has one of the following:

- A treatment side with a compromised dressing at 6 hours
- A subject who was not compliant to study requirements during the time between the 10 minute and 6-hour sample collection

CDT

A treatment side might also be excluded for scrub time or sample times outside of the approved window.

All deviations not captured above that will result in exclusion from the PP analysis will be defined and justified in a blinded fashion. In addition, documentation will be made of these data classification decisions prior to data lock.

6. GENERAL STATISTICAL CONSIDERATIONS

All statistical analyses will be performed using SAS version 9.4 or above (SAS Institute, Cary, NC). Any changes to the methods proposed in this SAP will be documented in the “Changes to Planned Analyses” section of the final clinical investigation report.

Reporting Precision:

- Age will be reported as whole years.
- $\text{Log}_{10} \text{ CFU/cm}^2$ and reduction \log_{10} will be reported to 2 decimal places.
- Means and medians will be presented to one more degree of precision than the raw data; except when specified otherwise.
- Standard deviations and standard errors will be presented to two more degrees of precision than the raw data except when otherwise specified.
- For log recovery and log reduction, means and medians will be reported to 2 decimal places and the standard deviation to 3 decimal places.
- Minimums and maximums will be presented to the same degree of precision as the raw data.
- Confidence limit boundaries will be presented to one more degree of precision than the raw data.
- P-values will be rounded to 3 decimal places and presented as 0.xxx. P-values smaller than 0.001 will be presented as “<0.001.” P-values greater than 0.999 will be presented as “>.999”.

CDT

- Fractional numeric values will be presented with a zero to the left of the decimal point (for example, 0.12 – 0.30).
- Percentages (such as return to baseline percentage) will be presented to one decimal place.

Other Data Handling Issues:

- On treatment day, when a plate at the lowest dilution (highest concentration of bacteria) has no observed colonies, a value of “1” will be used, consistent with standard microbiology.

Process time limits:

- 10-minute post-prep sampling time (post-prep and 3-minute dry) 10 minutes \pm 30 second.
- 6-hour post-prep sampling time (post-prep and 3-minute dry) 6 hours \pm 30 minutes.
- The microbiological samples must be plated within 30 minutes of sample collection.

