##### Modified Sampling Solution (MSS):

A sterile scrub cup will be placed and held firmly on each site. **Scrub 1:** 1.0 mL of Triacetin and 2.0 mL of SSS will be aseptically pipetted into the scrub cup. The skin will be scrubbed in a circular motion with moderate pressure for 1 minute using a sterile policeman. Using a sterile transfer pipette, the scrub solution will be transferred to a sterile collection tube. **Scrub 2:** An additional 3.0 mL of fresh SSS will be pipetted into the scrub cup and the scrub procedure will be repeated. This solution will be pooled with the solution from Scrub 1 for a total sample volume of approximately 6 mL per site.

Following collection, each sample tube will be capped tightly and pulsed 3 times on a vortex mixer followed by a 2-minute sonication and 30-second vortex. A 1.0 mL aliquot of each sample will be diluted into sterile tubes containing 9.0 mL PBW. Serial 10-fold dilutions will be performed in PBW. One-milliliter (1.0-mL) aliquots of selected dilutions will be pour-plated in triplicate using TSA+N. **Samples must be plated within 30 minutes of collection. Plated samples must be well swirled.** Each plate should be labeled with the subject treatment number, anatomical region sampled (groin), test site sampled (right or left and time point), and dilution plated. After 72 ( $\pm$  4) hours of aerobic incubation at  $30 \pm 2^\circ\text{C}$ , colonies will be counted and viable cells in the original sample will be calculated using standard methods. Following incubation, plates may be refrigerated for up to 48 hours prior to counting.

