**[name]**

Based on the scrub and dilution process, in order to have a baseline  $\geq 5.0 \log_{10}$  requires that the average of the 3 plates from the  $10^{-3}$  dilution be  $\geq 63$ . Averaging of the Screening Day counts will be automatically performed on the eCRF upon entry of raw data and Clindex will determine the subject's eligibility for treatment.

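### The zero-colony rule is worded per plate although samples are plated in triplicate, so it distorts the lowest counts and, if empty plates are common, can favour non-inferiority

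*SAP*

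**What the plan says.** For Treatment Day counts, SAP section 6 (Other Data Handling Issues) has a rule that is triggered "when a plate at the lowest dilution (highest concentration of bacteria) has no observed colonies". In that event, the SAP states, "a value of “1” will be used, consistent with standard microbiology". The unit of the 1 is not given. It could be one colony on that plate, a sample mean of 1, or one colony over all plates. Nor does the SAP say whether substitution comes before or after plates are combined.

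In Protocol 5.3.4.1 the two scrubs are pooled "for a total sample volume of approximately 6 mL per site", diluted tenfold in series, and 1.0 mL "aliquots of selected dilutions will be pour-plated in triplicate using TSA+N". Which dilutions are selected is not stated. The same section says that "colonies will be counted and viable cells in the original sample will be calculated using standard methods".

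Protocol 5.3.4.2 explains that a baseline of 5.0 log10 "requires that the average of the 3 plates from the" 10⁻³ dilution reach 63. It adds: "Averaging of the Screening Day counts will be automatically performed on the eCRF". No matching sentence covers Treatment Day, so averaging there is an inference from triplicate plating and the baseline threshold.

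**The concern.** The 10-minute log10 recovery is the response in the primary regression (SAP 8.1), so this rule is part of how the primary variable is derived. With three plates per dilution, the smallest non-zero mean is one colony over three plates, or 0.33. A substituted value of 1 lies above that, so the rule can overwrite real low counts or reverse their order.

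The affected samples are the cleanest ones, which come mainly from the two active products. Raising them pulls both product means toward a common floor. If SoluPrep were truly worse than SoluPrep FF, the estimated difference would be too small. Against a 0.5 log10 margin, that error favours a non-inferiority conclusion.

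**Working it through.** **Inputs from the documents.** Sample volume about 6 mL and 1.0 mL plated, in triplicate (Protocol 5.3.4.1); cup area 3.80 cm² (Protocol 3.4.4); SD 1.0, 100 observations per active product, margin 0.5, one-sided alpha 0.025 (SAP 6.2).

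**Inputs assumed.** The lowest plated dilution and the mean 10-minute recovery of the active products are not stated, so a range of each is shown.

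**Reproducing the plan's figures.**
- Power: SE = 1.0 × √(2/100) = 0.1414; 0.5/0.1414 − 1.96 = 1.576; Φ(1.576) = 0.942, matching the stated 94%.
- Plate conversion: log10(mean count × 10^d × 6/3.80), where d is the number of tenfold dilutions. A mean of 63 at d = 3 gives 4.998, matching the 5.0 threshold in Protocol 5.3.4.2.

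**Scores for small triplicates**, log10/cm², undiluted sample (add 1.00 for 10⁻¹):

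| Plates | Raw mean | 1 for each empty plate | Mean of 1 if all empty | Total of 1 if all empty |
|---|---|---|---|---|
| (0,0,0) | undefined | 0.20 | 0.20 | −0.28 |
| (0,0,1) | −0.28 | 0.20 | −0.28 | −0.28 |
| (0,1,1) | 0.02 | 0.20 | 0.02 | 0.02 |
| (0,0,2) | 0.02 | 0.32 | 0.02 | 0.02 |
| (1,1,1) | 0.20 | 0.20 | 0.20 | 0.20 |

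The per-plate reading raises (0,0,1) by log10(3) = 0.48 and makes four different results identical. The all-empty reading with a mean of 1 puts a sterile sample 0.48 above a sample with one colony. The last column has neither fault.

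**Effect on the product difference.** True log10 densities were simulated as normal with SD 1.0, with SoluPrep 0.50 above SoluPrep FF and Poisson counts on three plates (400,000 samples per product). The chance of wrongly concluding non-inferiority is Φ((0.5 − D)/(s√(2/100)) − 1.96), where D and s are the estimated difference and SD after the rule; its nominal value is 0.025. Pooled means a total of 1 only if all three plates are empty. The simulation is an independent two-sample comparison and leaves out the baseline covariate.

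| Lowest dilution | SoluPrep FF mean | Samples with an empty plate | D: per plate / pooled | False non-inferiority: per plate / pooled |
|---|---|---|---|---|
| 10⁻¹ | 2.0 | 27% | 0.42 / 0.47 | 0.09 to 0.10 / 0.04 |
| 10⁻¹ | 2.5 | 14% | 0.47 / 0.49 | 0.043 / 0.028 |
| 10⁻¹ | 3.0 | 6% | 0.49 / 0.50 | 0.030 / 0.025 |
| undiluted | 2.0 | 6% | 0.49 / 0.50 | 0.029 / 0.024 |
| undiluted | 3.0 | 0.6% | 0.50 / 0.50 | 0.025 / 0.026 |

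The range in the first row is the spread between repeated runs. The all-empty reading with a mean of 1 falls between the two rules (0.44 and about 0.06 in the first row). One tenfold dilution is equivalent to a shift of 1 log10 in the mean, so undiluted plating at a mean of 1.0 behaves like the first row.

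**Other endpoints.** Against saline, raising active counts reduces the saline-minus-active contrast, which is conservative. At 6 hours the substituted values (0.20 undiluted, 1.20 at 10⁻¹) lie far below the minimum eligible baseline of 5.00, so return to baseline is practically unaffected.

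**The case against.** The strongest reply is that the damaging case is assumed. No section says the lowest post-prep plate is 10⁻¹. The neutralization validation (Appendix 14.9.7.2) plates inoculated scrub samples without serial dilution, which fits undiluted plating, though it does not establish it for the main study.

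The documents' own anchors also suggest higher recovery. Baselines run from 5.00 to 7.50 (SAP 5.2), and the effect over saline was about 2.5 (SAP 6.2). Assuming a mean baseline of 5.5 to 6.25 and a saline reduction of 0 to 0.5, active recovery is 5.5 − 0.5 − 2.5 = 2.5 up to 6.25 − 0 − 2.5 = 3.75. A mean of 2.0 would need, for example, a baseline of 5.5 and a saline reduction of 1.0. This stands, and it limits the size of the point.

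It also stands that some floor is unavoidable, because log10(0) is undefined. In the worst row, 0.03 of the 0.08 shrinkage remains with pooled plates (0.50 − 0.47), so the rule's excess is 0.05 (0.47 − 0.42).

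A reader might infer three stronger claims that the documents do not support:
- That the rule biases the primary comparison outright. Shrinkage needs a real product difference together with a material share of empty plates, and neither is established.
- That every reading of the rule is wrong. One colony in total is a possible reading and is sound.
- That identical sterile samples will score 1 log10 or more apart. That requires the lowest dilution to vary between samples, which Protocol 5.3.4.1 neither states nor excludes.

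The appeal to standard practice does not settle the matter, because the standard method is not spelled out and the SAP's wording refers to a single plate.

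**Conclusion.** The concern holds in conditional form. The distortion of individual low counts follows from arithmetic: up to 0.48 log10 if the rule is followed as worded, or a rank reversal if it is applied as a mean of 1 to all-empty samples. Both rest on Treatment Day plates being averaged, which is inferred.

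The effect on the non-inferiority comparison depends on two quantities that the documents do not give. It is material in the low-recovery corner (10⁻¹ lowest dilution, mean near 2.0), where the chance of a false non-inferiority finding at the margin is about 0.09 to 0.10, against about 0.04 with pooled plates. It is small at means of 2.5 to 3.0, and negligible if undiluted sample is plated and mean recovery is 2.0 or more. The plan should be changed because the direction favours the sponsor's conclusion and the correction is nearly free. The point does not show that the trial's conclusion would be wrong.

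**What to change.** In SAP section 6, derive the count from the total colonies on the three plates at the lowest dilution. Substitute a total of 1 (a mean of 0.33) only when that total is zero, and state that the same derivation applies to all Treatment Day samples.

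In Protocol 5.3.4.1, name one lowest plated dilution common to all 10-minute and 6-hour samples of the two active products, so that they share one floor. Requiring undiluted plating for every product, saline included, goes further than this point needs.

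The cost is one sentence in each document and one line in the derivation program. Three extra plates per post-prep sample are needed only where the laboratory would not already plate the named dilution. Both changes should be settled before data lock, because choosing the rule after unblinding would be a data-dependent decision on the primary variable.
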